### Study protocol

A list of patients who had gone through trauma splenectomy or bowel resection due to bowel obstruction in our center between July 2008 and July 2013, was made. Patients were divided into two groups: trauma splenectomy (exposed group) and bowel resection (unexposed group).

All patients were followed up for 5-10 years.

Our study criteria was as follows:

Exclusion criteria:

1. Disturbed lipid profile at the time of surgery, 2. Disturbed blood glucose levels at the time of surgery, 3. History of high blood pressure prior to surgery, 4. Use of any hyperglycemic agent during the follow up period, 5.  $BMI \geq 25$  at the time of surgery, 6. History of diseases potentially affecting blood glucose, e.g. hyperthyroidism, Cushing syndrome, 7. Accidental pancreatic damage during surgery, 8. Resection of  $>10$  cm of small bowel and 9. History of malignancy or radiotherapy (criteria 8 and 9 were specific to unexposed group).

Patients were contacted through phone calls. Of the 243 splenectomized patients, 90 patients who met our study criteria were willing to participate. Of 152 patients with bowel resection, 64 were willing to participate. Records of patients at the time of surgery were retrieved from hospital archive of patients' records. Patients were invited to an office meeting for assessment of blood pressure, BMI and a general physical examination and history taking. An appointment was made for drawing blood samples for measurement of lipid profile, Hb A1C and fasting blood sugar.

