### Statistical analysis

After completion of data collection, data were entered in Excel and analyzed using SPSS software for Microsoft (version 22).

Student's t-test was used to compare the mean value of measured variables between the two groups. Chi-squared test was used to assess the relation between family history of diabetes mellitus (DM) and developing DM among participants. P value of  $< 0.05$  was considered significant.

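### The chi-squared test of family history against diabetes is run across two surgical cohorts without stratifying by operation; a stratified test is a minor, cheap improvement

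*Protocol*

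**What the plan says.** The protocol's Study protocol section defines the sample by operation: "Patients were divided into two groups: trauma splenectomy (exposed group) and bowel resection (unexposed group". The numbers enrolled are given as "Of the 243 splenectomized patients, 90 patients who met our study criteria were willing to participate" and "Of 152 patients with bowel resection, 64 were willing to participate", so 90 + 64 = 154 participants. On follow-up it says only "All patients were followed up for 5-10 years", without a breakdown by group.

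The Statistical analysis section names two tests. The t-test compares means between the two groups. The other is described as follows: "Chi-squared test was used to assess the relation between family history of diabetes mellitus (DM) and developing DM among participants". A P value below 0.05 "was considered significant". For the second test no stratification or adjustment by operation is mentioned. Because the t-test is tied to the two groups and the chi-squared test is tied to participants, one table over everyone is the natural reading, though the document does not say so outright.

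The document gives no family-history rate, DM rate, odds ratio or power.

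**The concern.** A single table mixes two things: the relation between family history and DM inside each operation, and the difference between the operations. If patients with one operation have both more family history and more DM, the table shows an association even when none exists within either group. If the gaps run in opposite directions, a real within-group relation is diluted.

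Nothing in the described selection balances family history. There was no randomisation or matching, participation was voluntary (90 of 243 and 64 of 152), and two exclusion criteria applied to one cohort only. A DM difference between an exposed and an unexposed cohort is also quite possible. The conclusion at stake is whether family history is credited or discredited as a correlate of DM in these patients, in one of only two analyses that the protocol names.

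**Working it through.** **Inputs.** From the protocol: n = 90 (splenectomy) and 64 (resection), and significance at 0.05. Assumed, because the document gives no figures: family history 20-40% by group; DM 5-20% v 5% under no relation; and for power a common within-group odds ratio of 3, with the stated DM rate being the rate without family history. There is no figure of the plan's own to reproduce.

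**Method.** Each group's 2x2 table was simulated (20,000 to 200,000 data sets per scenario). The uncorrected pooled Pearson chi-squared test was compared with the uncorrected Cochran-Mantel-Haenszel (CMH) test stratified by operation, at two-sided 0.05. Pooled odds ratios come from expected counts. All pairs below are splenectomy/resection.

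**How pooling creates an association.** Take family history 40/20%, DM 20/5%, and no relation inside either group.
- With family history: 90 × 0.40 + 64 × 0.20 = 48.8 patients. DM: 36 × 0.20 + 12.8 × 0.05 = 7.84; no DM: 40.96.
- Without: 54 + 51.2 = 105.2 patients. DM: 54 × 0.20 + 51.2 × 0.05 = 13.36; no DM: 91.84.
- Pooled odds ratio: (7.84 × 91.84) / (40.96 × 13.36) = 1.32, although it is 1 in each group.

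**False-positive rate, no relation within groups**

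| Family history | DM | Pooled | CMH |
|---|---|---|---|
| 25/25% | 20/5% | 4.9% | 4.8% |
| 40/20% | 20/20% | 5.1% | 5.1% |
| 30/20% | 10/5% | 5.3-5.5% | 4.6% |
| 30/20% | 15/5% | 6.1% | 4.9% |
| 30/20% | 20/5% | 6.7-6.8% | 4.9-5.0% |
| 40/20% | 10/5% | 6.1-6.2% | 4.7% |
| 40/20% | 20/5% | 9.5-9.7% | 4.9-5.0% |

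Where a range is shown, separate runs differed by simulation error. The first two rows show that a gap in one variable alone leaves the level intact.

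**Power, within-group odds ratio 3**
- Opposing gaps (family history 20/40%, DM 12/4%): pooled 37%, CMH 54%, a relative loss of (54 − 37)/54 = 31%. Expected pooled table: 8.07 and 35.53 with family history, 10.18 and 100.22 without. Pooled odds ratio (8.07 × 100.22)/(35.53 × 10.18) = 2.24.
- Same-direction gaps (40/20%, 15/5%): pooled 83%, CMH 67%. The extra rejections come from bias, since the pooled odds ratio is 3.64.
- No gap (25/25%, 8/8%): pooled 57%, CMH 56%.
- Lower DM rates (8/4%): CMH power is 49% with family history 25/25% and 47% with 20/30%.

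**Cost of stratifying**
- No gap in either variable: about 0-1 point.
- Family history differs by 20 points and DM without family history is 8% in both: pooled 60% v CMH 58% for 40/20%, and 59% v 56% for 20/40%, so about 3 points.
- Family history 25/25%, DM 8/8%: pooled 57%, exact conditional 50%, continuity-corrected CMH 46%. With DM 12/4%: pooled 56%, exact 51%, corrected 47%. At higher rates (family history 30%, overall DM 20% in both groups) the corrected version takes 75.4% to 68.0%. The exact or corrected form thus costs about 5-10 points.

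**The case against.** **The document does not say one pooled table, and the detail may sit in an analysis plan that is not shown.** The first part is true as a matter of wording, but the contrast with the t-test makes pooling the natural reading. On the second, the protocol itself names this test, so the point concerns a stated choice rather than missing detail.

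**A chi-squared test of the marginal relation is valid for the marginal relation.** This stands. The excess rejections are false positives only if the question is about the relation within operations. In a sample made of two cohorts that is the more useful question, but the document does not state its target.

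**No reason is given for a large family-history gap.** This largely stands. If true prevalence were 25% in both groups, the standard error of the difference would be √[0.25 × 0.75 × (1/90 + 1/64)] = 7.1 points, so a chance gap of 20 points or more has probability of about 0.5%. A systematic gap of that size is possible, but the document neither gives nor implies one.

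**Stronger readings that a reader might infer.** One is that the planned test doubles the false-positive rate or loses a third of its power. Those figures belong to the extreme assumed scenarios, with large gaps in both variables and, for the power loss, in opposing directions. Another is that stratifying is free, which the costs above contradict. A third is that it fully repairs the analysis. It removes confounding by operation only; age and the 5-10 year spread of follow-up remain. Finally, the text at hand states no study aim, so it does not establish that the cohorts were assembled because DM risk was expected to differ.

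**Conclusion.** The point holds as a minor one. As written, the test ignores operation in a sample of two non-randomised cohorts, and it is confounded if family history and DM both differ between them. Under assumed modest family-history gaps (30% v 20%) the false-positive rate is about 5-7%. Under 40% v 20% with DM 20% v 5% it is about 10%. With opposing gaps (20% v 40%, DM without family history 12% v 4%, odds ratio 3) power is 37% rather than 54%. If only one variable differs, the level is unaffected. All these sizes rest on assumed rates; only the group sizes and the 0.05 threshold come from the protocol. Nothing in the document shows that the family-history result is in fact biased.

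**What to change.** In the Statistical analysis section, replace the single chi-squared test with a sentence to this effect: *the relation between family history and DM is tested with a Cochran-Mantel-Haenszel test stratified by operation, without continuity correction; the common odds ratio with its 95% confidence interval and the two group-specific tables are reported.* The group-specific tables let the reader judge whether a common odds ratio is reasonable.

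State which version of the test is used and check that the software output matches it, because the choice affects power more than the stratification does. If an exact version is wanted for very few DM cases (at 5%, 64 × 0.05 = 3.2 expected in the resection group), say so in advance and accept its power cost.

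The change takes one sentence, uses data already collected and needs no extra patients. The report should add that age and length of follow-up are not accounted for.
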